6.2.5 Local Site Pain

Local site pain will be assessed using 100 mm VAS immediately (within 15 minutes) after study drug administration (Day 1) according to the schedule of assessments ([Table 10-1](#)). Subjects will be asked to indicate their current level of pain intensity by drawing a single vertical line (|) on the 100 mm line ([Appendix 10.2](#)).

6.3 Sample Collections, Storage and Shipment

6.3.1 Sample Collections

The total volume of blood collected for each assessment is discussed in each specific laboratory manual. The sample collection tube may be changed during the study and details will be provided in the laboratory manual.

6.3.1.1 Pharmacokinetic Sampling

Blood will be collected per blood sampling time points for PK assessment sample at the time points specified in the schedule of assessments ([Table 10-1](#)). All samples will be collected as close as possible to the scheduled time point, and the actual sampling time will be recorded. Explanation will be provided in the eCRF for missed or mishandled samples and for samples collected outside the specified time windows.

Samples should be stored and shipped as detailed in the laboratory manual.

6.3.1.2 Interferon- γ Release Assay

Blood samples for IGRA will be obtained at the time points specified in the schedule of assessments ([Table 10-1](#)).

6.3.1.3 Clinical Laboratory Testing

Blood samples for routine safety (clinical laboratory testing) will be collected for analysis throughout the study at the time points specified in the schedule of assessments ([Table 10-1](#)).

An additional blood for hepatitis B and C, HIV (HIV-1, HIV-2) and nontreponemal tests will also be required at Screening. A serum pregnancy test sample will be required at Screening and at the EOS visit for women of childbearing potential who have not been surgically sterilized.

6.3.1.4 Immunogenicity Sampling

Blood samples for immunogenicity assessments will be obtained at the time points specified in the schedule of assessments ([Table 10-1](#)).

Samples should be stored and shipped as detailed in the laboratory manual.

6.4 Labeling, Storage, and Transportation of Samples

6.4.1 Sample Labeling

Each sample tube will be clearly labeled with the following information: study number, subject number, tube identification, and scheduled sampling time point.

6.4.2 Sample Storage and Shipment

During the study, blood samples will be collected for PK and immunogenicity, analyses.

Where appropriate, the serum should be transferred into a sufficient number of transfer tubes for transport to assigned testing facilities. Primary and back-up samples will be shipped to the central laboratory according to the laboratory manual, and primary samples should be shipped separately from the back-up samples.

Additionally, back-up samples for PK and immunogenicity should be retained at the central laboratory as a backup for up to 5 years after the end of the study in case additional analysis is required. If additional analysis for PK and immunogenicity is not required, the samples will be stored at CELLTRION, Inc. or a designated biobank for a further 5 years (from the date the sample is transferred to the biobank) unless a specific authorization is given by CELLTRION, Inc. to destroy the sample. Additional tests can be conducted at CELLTRION, Inc. or the biobank if it is required from a regulatory or medical perspective. Details in storage and shipment will be followed according to the laboratory manual.

7 Statistical Analysis Plan

The statistical analysis will be performed using [REDACTED]

[REDACTED] The statistical methods for this study will be described in a detailed statistical analysis plan (SAP), which will be finalized before locking of the database. Changes from analyses planned in this protocol will be documented in the SAP. Any deviations from the planned analysis as described in the SAP will be justified and recorded in the final clinical study report (CSR).

For categorical variables, frequencies and percentages will be presented. Continuous variables will be summarized using descriptive statistics (number of subjects, mean, standard deviation [SD], median, minimum, and maximum).

7.1 Study Population

7.1.1 Disposition of Subjects

The number and percentage of subjects entering and completing the clinical study will be presented by treatment arm.

The number of subjects who enroll in the study and the number and percentage of subjects who complete the study will be presented. Frequency and percentage of subjects who withdraw or discontinue from the study, and the reason for withdrawal or discontinuation, will also be summarized.

7.1.2 Protocol Deviations

Deviations from the protocol, including deviations of inclusion/exclusion criteria, will be defined as “minor” or “major” before overall code breaking.

7.1.3 Analysis Populations

Intent-to-treat (ITT) Population: The ITT population is defined as all subjects enrolled and randomly assigned to receive a dose of any study drug, regardless of whether or not any study drug dosing was completed. Subjects will be assigned to treatment arms based on randomization.

All study population analyses, including disposition of subjects, protocol deviations, and analysis populations as well as demographic and background characteristics will be analyzed using the ITT Population.

Pharmacokinetic Population: The PK population will include subjects who receive a complete dose of study drug and provide at least 1 post-treatment serum concentration with a concentration above the lower limit of quantification. Subjects in the PK population will be analyzed according to the treatment they received.

Safety Population: The safety population will include all randomized subjects who receive a complete or partial dose of study drug. Subjects will be assigned to treatment arms based on treatment actually received.

7.2 Pharmacokinetic Analyses

All PK analyses will be conducted based on the PK population. The primary and secondary PK parameters of CT-P17 and adalimumab will be analyzed using non-compartmental methods based on the actual sampling time points. All parameters will be calculated using

7.2.1 Primary Pharmacokinetic Analyses

The primary PK parameters, $AUC_{0-\text{inf}}$, $AUC_{0-\text{last}}$, and C_{\max} , will be presented in data listings and summarized by treatment using the following descriptive statistics: number of subjects, mean, SD, median, minimum, maximum, geometric mean, and coefficient of variation (CV). Additionally, primary PK parameters will be summarized by treatment and anti-drug antibody status.

For primary endpoints, the statistical analysis of the log-transformed primary endpoints ($AUC_{0-\text{inf}}$, $AUC_{0-\text{last}}$, and C_{\max}) will be based on an analysis of covariance model with treatment as a fixed effect and body weight (≥ 80 kg vs. < 80 kg) as measured on baseline (Day -1), gender (male vs. female) and study center as covariates. The similarity of PK between CT-P17 vs. US-licensed Humira, CT-P17 vs. EU-approved Humira, and US-licensed Humira vs. EU-approved Humira will be concluded if the 90% CIs for ratios of geometric means of each comparison are entirely contained within 80% to 125% for $AUC_{0-\text{inf}}$, $AUC_{0-\text{last}}$, and C_{\max} .

7.2.2 Secondary Pharmacokinetic Analyses

Serum concentration data will be presented in data listings and summarized by time point for each treatment using the following descriptive statistics: number of subjects, mean, SD, median, minimum, maximum, geometric mean, and CV.

The secondary PK parameters, %AUC_{extrap}, T_{max}, V_z/F, λ_z, t_{1/2}, and CL/F, will be also presented in data listings and summarized by treatment using the following descriptive statistics: number of subjects, mean, SD, median, minimum, maximum, geometric mean, and CV.

Additional PK analyses may be performed as detailed in the SAP.

7.3 Safety Analyses

7.3.1 Demographic, Baseline, and Background Characteristics

Baseline demographic and background variables will be summarized by treatment arm using the ITT population.

Demographics (including age, gender, ethnicity and race) and baseline and background characteristics will be presented in summary tables. Qualitative data (e.g., medical history) will be summarized in contingency tables, and quantitative data (e.g., age) will be summarized using quantitative descriptive statistics.

7.3.2 Adverse Events

Adverse events will be recorded according to the CTCAE v5.0 and will be coded to system organ class (SOC) and preferred term (PT) according to MedDRA. A TEAE is defined as described in [Section 6.2.1.1](#). The following AE summaries will be reported by SOC, PT, and treatment arm, as appropriate:

- Number and percentage of subjects reporting at least 1 TEAE
- Number and percentage of subjects reporting at least 1 treatment-emergent SAE
- Number and percentage of subjects discontinuing the study drug due to a TEAE
- Number and percentage of subjects with AESIs (injection site reactions, hypersensitivity/allergic reactions, infections, and malignancies)

All AE data will be presented in the data listings, and additional TEAE analyses may be performed as detailed in the SAP.

7.3.3 Immunogenicity Analysis

Immunogenicity test results will be summarized by treatment arm and presented in a data listing.

7.3.4 Clinical Laboratory Test

Actual values and changes from Baseline for clinical laboratory test results will be summarized by treatment arm at each time point using descriptive statistics (number of subjects, mean, SD, median, minimum, and maximum). Shift tables will be generated for clinical laboratory test results.

Individual clinical laboratory test results will be presented in data listings.

7.3.5 Electrocardiogram, Physical Examination, and Vital Signs

Actual values and change from Baseline for vital sign measurements will be summarized by treatment arm at each time point using descriptive statistics (number of subjects, mean, SD, median, minimum, and maximum).

Shift tables comparing the categorical investigator interpretation of 12-lead ECGs and physical examinations at each scheduled post-baseline time point with those at Baseline will be summarized by treatment arm.

Individual 12-lead ECG results and the investigator's interpretation, physical examination findings, and vital sign measurements (including hypersensitivity monitoring) will be presented in data listings.

7.3.6 Tuberculosis Assessments

Results from TB screening and monitoring will be summarized by treatment arm and presented in data listings.

7.3.7 Local Site Pain

Individual local site pain (VAS) results will be summarized by treatment arm after the study drug administration using descriptive statistics (number of subjects, mean, SD, median, minimum, and maximum).

Individual local site pain (VAS) results will be presented in a data listing.

7.3.8 Prior and Concomitant Medications

Prior and concomitant medications will be coded using the WHO Drug Dictionary (WHO-DD). All prior and concomitant medications data will be listed and summarized by treatment arm as appropriate.

7.4 Sample Size Calculations

A sample size of 91 subjects from each arm will provide at least 90% power to show similarity in PK; CT-P17 vs. US-licensed Humira, CT-P17 vs. EU-approved Humira and US-licensed Humira vs. EU-approved Humira using 90% CI approach based on 80% to 125% equivalence margin, expected geometric mean ratio of 1.0 and CV of 48%, which is assumed based upon historical PK data in healthy subjects.

The sample size is calculated from a two one-sided alpha level of 0.05. Approximately 306 enrolled subjects (102 in each arm) are expected to yield at least 273 evaluable subjects (91 in each arm) with a 10% drop-out rate. By assuming that the primary PK parameters are highly correlated, the Type I/II error adjustment for multiplicity correction is not considered.

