A sample size of 91 subjects from each arm will provide at least 90% power to show similarity in PK of the followings; CT-P17 vs. US-licensed Humira, CT-P17 vs. EU-approved Humira and US-licensed Humira vs. EU-approved Humira using 90% confidence interval (CI) approach based on 80% to 125% equivalence margin, expected geometric mean ratio of 1.0, and coefficient of variation (CV) of 48%, which is assumed based upon historical PK data in healthy subjects.

The sample size is calculated from a two one-sided alpha level of 0.05. Approximately 306 enrolled subjects (102 in each arm) are expected to yield at least 273 evaluable subjects (91 in each arm) with a 10% drop-out rate. By assuming that the primary PK parameters are highly correlated, the Type I/II error adjustment for multiplicity correction for PK parameters is not considered.

Statistical Analyses:

Pharmacokinetic analysis: The statistical analysis of the log-transformed primary endpoints (AUC_{0-inf}, AUC_{0-last}, and C_{max}) will be based on an analysis of covariance model with covariate(s). The similarity of PK between; CT-P17 vs. US-licensed Humira, CT-P17 vs. EU-approved Humira, and US-licensed Humira vs. EU-approved Humira will be concluded if the 90% CIs for ratios of geometric means of each comparison are entirely contained within 80% to 125% for AUC_{0-inf}, AUC_{0-last}, and C_{max}. The PK endpoints will be calculated using non-compartmental methods. The PK analysis will be conducted based on the PK population.

Pharmacokinetic parameters will be presented in data listings and summarized in tables. The tables will display the following descriptive statistics: number of subjects, mean, standard deviation, median, minimum, maximum, geometric mean, and CV.

For secondary endpoints, following PK parameters will be assessed: %AUC_{extrap}, T_{max}, V_z/F, λ_z, t_{1/2}, and CL/F.

Additional PK analyses may be performed as detailed in the statistical analysis plan.

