2.1 Primary Objective

- To demonstrate the PK similarity in terms of $AUC_{0-\text{inf}}$, $AUC_{0-\text{last}}$, and C_{\max} of CT-P17, US-licensed Humira, and EU-approved Humira in healthy subjects (CT-P17 to US-licensed Humira, CT-P17 to EU-approved Humira, and US-licensed Humira to EU-approved Humira)

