3.1 Study Design

CT-P17 is being developed as a proposed biosimilar of Humira (adalimumab). This study is a phase 1, randomized, multicenter, double-blind, three-arm, parallel group, single-dose, active comparator study, which is designed to demonstrate equivalence in PK of CT-P17 to US-licensed Humira and EU-approved Humira in healthy subjects. Approximately 306 subjects will be enrolled and randomly assigned to one of the three treatment arms in a 1:1:1 ratio. In each treatment arm, all subjects will receive a single dose (40 mg) of either CT-P17, US-licensed Humira, or EU-approved Humira by SC injection via PFS on Day 1 followed by 10 weeks during which PK, safety, and immunogenicity measurements will be made. The randomization to treatment assignment will be stratified by body weight (≥ 80 kg vs. < 80 kg) as measured on Day -1, gender (male vs. female) and study center.

A schematic of the study design is presented in [Figure 3-1](#). Refer to [Section 3.2](#) for the study overview, including procedures to be performed during the study.

Figure 3-1 **Study Design Overview**

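### The stated 90% power is for one pairwise comparison; at the plan's own inputs, power is about 83% for the two CT-P17 comparisons and 78% for all three

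*Protocol*

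**What the plan says.** Protocol 7.4 states "A sample size of 91 subjects from each arm will provide at least 90% power to show similarity in PK" and names CT-P17 against US-licensed Humira, CT-P17 against EU-approved Humira, and US-licensed against EU-approved Humira, with 'and' before the last. SAP 5.1 repeats this. The Sample Size paragraph of the synopsis has the same claim: "A sample size of 91 subjects from each arm will provide at least 90% power to show similarity in PK of the followings". The inputs are limits of 80% to 125%, two one-sided tests at 0.05, and "expected geometric mean ratio of 1.0 and CV of 48%, which is assumed based upon historical PK data in healthy subjects".

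Protocol 2.1 puts all three pairs into one primary objective: "in healthy subjects (CT-P17 to US-licensed Humira, CT-P17 to EU-approved Humira, and US-licensed Humira to EU-approved Humira". Protocol 3.1 and SAP 4.1 describe a narrower aim, a study "designed to demonstrate equivalence in PK of CT-P17 to US-licensed Humira and EU-approved Humira in healthy subjects". Under Protocol 7.2.1, similarity "will be concluded if the 90% CIs for ratios of geometric means of each comparison are entirely contained within 80% to 125" per cent, for AUC0-inf, AUC0-last and Cmax.

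On multiplicity, Protocol 7.4 says: "By assuming that the primary PK parameters are highly correlated, the Type I/II error adjustment for multiplicity correction is not considered". The synopsis limits this to endpoints: "the Type I/II error adjustment for multiplicity correction for PK parameters is not considered".

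Neither document says that 90% applies to each comparison separately, and neither gives a joint power.

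**The concern.** Power for a conclusion that needs several tests to succeed together is lower than power for any one of them. A reader who sees 90% attached to three comparisons, under an objective that names the same three, will infer a 10% chance of missing that objective when the products are truly identical. If 90% is really single-comparison power, the chance is more than twice that. The only reason given for ignoring Type II multiplicity is that the PK parameters are highly correlated. That says nothing about three treatment contrasts, which are correlated only because they share arms.

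The risk falls on the sponsor. Since every test must pass, false-positive error is not inflated and no similarity conclusion becomes unsafe. What is at stake is whether the stated power matches what the design delivers for its stated objective, in a study of about 306 healthy subjects for whom no therapeutic benefit is intended.

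**Working it through.** **Inputs (Protocol 7.4, SAP 5.1).** n = 91 evaluable per arm; CV = 0.48; true geometric mean ratio 1.0; limits 0.80 to 1.25; α = 0.05 for each one-sided test; 10% drop-out; allocation 1:1:1.

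**1. Reproducing the plan's figure: one comparison, one endpoint.**

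- Log-scale SD: σ = √ln(1 + 0.48²) = 0.4553.
- Standard error of a difference in log means: SE = 0.4553 × √(2/91) = 0.0675.
- Normal approximation: power = 2Φ(ln 1.25 / SE − 1.645) − 1 = 2Φ(0.2231/0.0675 − 1.645) − 1 = 2Φ(1.66) − 1 ≈ 0.903.
- Exact two one-sided tests, integrating over the chi-square distribution of the variance estimate: 0.9007 with 180 df (two arms) and 0.9016 with 270 df (three-arm pooled variance).
- At n = 90 the exact figure (two-arm df) is 0.8969, so 91 is the smallest n that reaches 90% for a single comparison.
- Drop-out: 91/0.90 = 101.1, rounded up to 102 per arm; 3 × 102 = 306.

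So 91, 102 and 306 are all correct for one comparison on one endpoint, with no reserve for more.

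**2. Joint power across comparisons.** Three-arm trials were simulated with all true ratios 1.0, variance pooled over the arms (3n − 3 df) and one endpoint. One endpoint is equivalent to assuming that the three PK parameters are perfectly correlated with equal CV, which favours the plan. The contrasts share arms, so their correlation is built in.

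| Evaluable per arm, CV 48% | One comparison | Both CT-P17 comparisons | All three |
|---|---|---|---|
| 91 | 90% | 83% (82.8%) | 78% (77.7%) |
| 102 (no drop-out) | 94% | 88% | 85% |

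Using only the two arms in each comparison for its variance changes the n = 91 joint figures little: 82.5% and 77.4%. The chance of missing all-three success at n = 91 is 1 − 0.777 ≈ 22%. For scale only, 90% for all three at CV 48% corresponds to about 115 evaluable per arm.

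**3. Is the shortfall due to the endpoints?** Assume CVs of 48%, 42% and 33% for AUC0-inf, AUC0-last and Cmax (illustrative; the plan gives only 48%). Power for one comparison on all three endpoints is then 0.902, 0.900 and 0.895 at between-endpoint correlations of 0.99, 0.95 and 0.90. High correlation can therefore keep the per-comparison 90% roughly intact. The loss in step 2 comes from the number of treatment comparisons. Adding endpoints cannot raise the 78% if any endpoint has CV 48%.

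**4. Dependence on the CV.** Power for all three comparisons at n = 91:

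| Residual CV | 48% | 45% | 43% | 42.5% | 42% |
|---|---|---|---|---|---|
| Power | 0.776 | 0.849 | 0.888 | 0.898 | 0.905 |

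Break-even for 90% is near 42.4%. Moving from 48% to 42% requires covariates that explain 1 − ln(1 + 0.42²)/ln(1 + 0.48²) = 1 − 0.1625/0.2073 ≈ 21.6% of the log-variance.

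**5. Is a CV near 42% plausible?** Protocol 1.4 gives a 90% CI of 107.2 to 124.9 for AUC0-1344 in a 300-subject comparison of two Humira formulations. Assuming a 150/150 split, which is not stated: half-width = ln(124.9/107.2)/2 = 0.0764; SE = 0.0764/1.65 = 0.0463; σ = 0.0463/√(2/150) = 0.401; CV = √(exp(0.401²) − 1) ≈ 41.8%. This is not an endpoint of the present trial, and the model behind that interval is not given. It shows only that such a value is possible.

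**The case against.** Four points can be made for the plan.

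- **The sentence may mean 90% for each comparison.** Every input describes a pairwise test, and the rule in Protocol 7.2.1 speaks of each comparison. No text says that one failed pair voids the others. This reading is possible, and on it the figure is right. But the sentence does not say so and the objective groups all three. The design statement's narrower aim still gives only 83%. A decision rule worded per comparison does not turn the power claim into a per-comparison one.
- **The absence of a Type II adjustment is disclosed.** It is, in Protocol 7.4 and SAP 5.1. The reason given covers endpoints only, and the synopsis limits it to PK parameters explicitly. A reader cannot learn from it that joint power falls by about 12 points.
- **Covariate adjustment may recover the loss.** This is the strongest point. Protocol 5.1 calls weight and gender potential influences on PK, and the model adjusts for weight, gender and centre; SAP 12 moves to measured body weight. If 48% is an unadjusted CV and covariates explain 15% of log-variance (an assumption), power is about 90% for the two CT-P17 comparisons and 87% for all three; at 20% it is about 93% and 90%. The plan claims no such credit and does not say which CV it means. So the joint figures stand as conditional on a residual CV of 48%.
- **Nothing operational changes.** Agreed: Type I error, sample size, analysis and conclusions are untouched. That limits the seriousness but does not make the sentence correct.

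**Conclusion.** The concern holds. The stated power of at least 90% is correct for one comparison on one endpoint, but not for the three comparisons to which the sentence attaches it. With true ratios of 1.0, a residual CV of 48% and 91 evaluable subjects per arm, power is about 83% for the two CT-P17 comparisons and about 78% for all three. The chance of missing the full primary objective is then at least 22%, against an implied 10%. These joint figures already assume perfectly correlated endpoints; if 48% turns out to be a pre-adjustment CV, they understate power. The point should be fixed, but it is a reporting fault with a sponsor-side risk and no threat to the validity of a similarity conclusion.

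**What to change.** First establish whether the 48% CV is before or after adjustment for weight, gender and centre, and say so. Then amend Protocol 7.4, the Sample Size paragraph of the synopsis, and SAP 5.1 along these lines, if 48% is the residual CV:

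> At a residual CV of 48% and a true ratio of 1.0, 91 evaluable subjects per arm give 90% power for each pairwise comparison on an endpoint with that CV. Power to meet all three comparisons is about 78% if the endpoints are perfectly correlated, and no higher otherwise.

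If 48% is unadjusted, give the assumed residual CV and recalculate both figures; at about 42%, three-comparison power would be about 91%. Add that the decision not to adjust for multiplicity rests on correlation between PK parameters only and does not preserve 90% joint power.

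The cost is an edit in three places and possibly a less favourable stated figure. It needs no more subjects and no change to the analysis or decision rule.
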